10.13 APPENDIX 13: ABBREVIATIONS

AD:	atopic dermatitis
ADR:	adverse drug reaction
AE:	adverse event
AESI:	adverse event of special interests
ALT:	alanine aminotransferase
AST:	aspartate aminotransferase
BUN:	blood urea nitrogen
CI:	confidence interval
CIOMS:	Council for International Organizations of Medical Sciences
COPD:	chronic obstructive pulmonary disease
COVID-19:	Coronavirus Disease 2019
CPK:	creatine phosphokinase, creatine phosphokinase
CRSwNP:	chronic rhinosinusitis with nasal polyposis
CSU:	chronic spontaneous urticaria
CT:	computerized tomography
DTP:	direct to patient
ECG:	electrocardiogram
e-CRF:	electronic case report form
EOS:	end of study
EOT:	end of treatment
EU:	European Union
FSH:	follicle-stimulating hormone
GDPR:	General Data Protection Regulation
GPSP:	Good Postmarketing Study Practice
HBcAb:	hepatitis B core antibody
HBsAb:	hepatitis B surface antibody
HBsAg:	hepatitis B surface antigen
HBV:	hepatitis B virus
hCG:	human chorionic gonadotropin
HCV:	hepatitis C virus
HCVAb:	hepatitis C virus antibody
HIV:	human immunodeficiency virus
HRT:	hormonal replacement therapy
ICF:	informed consent form
ICH:	International Council for Harmonisation
IGAR:	interferon-gamma release assay
IgM:	immunoglobulin M
IL:	interleukin
IL-4R α :	interleukin-4 receptor alpha subunit
IMP:	investigational medicinal product
INCS:	intranasal corticosteroid
IRB:	Institutional Review Board

IVRS:	interactive voice response system
IWRS:	interactive web response system
LAR:	legally authorized representative
LMK:	Lund Mackay
mITT:	modified intention-to-treat
NC:	nasal congestion obstruction
NE:	nasal endoscopy
NERD:	nonsteroid anti-inflammatory drug exacerbated respiratory disease
NIMP:	noninvestigational medicinal product
NPS:	nasal polyp score
NSAID:	nonsteroid anti-inflammatory drug
OC:	osteomeatal complex
PCSA:	potentially clinically significant abnormality
PN:	prurigo nodularis
PP:	per protocol
PPE:	per protocol with extension term
PT:	preferred term
q2w:	every 2 weeks
q4w:	every 4 weeks
QTL:	quality tolerance limit
SAE:	serious adverse event
SAF:	safety population
SAFE:	safety population for extension term
SAP:	statistical analysis plan
SC:	subcutaneous
SCS:	systemic corticosteroid
SGOT:	serum glutamic-oxaloacetic transaminase
SGPT:	serum glutamic-pyruvic transaminase
SoA:	Schedule of Activities
SUSAR:	suspected unexpected serious adverse reaction
TB:	tuberculosis
TEAE:	treatment-emergent adverse event
TESAE:	treatment-emergent serious adverse event
TSS:	total symptom score
ULN:	upper limit of normal
US:	United States
VAS:	visual analogue scale
WBC:	white blood cell
WOCBP:	woman of childbearing potential
WOCF:	worst-observation carried forward

10.14 APPENDIX 14: PROTOCOL AMENDMENT HISTORY

Not applicable.

## VERSION HISTORY

This statistical analysis plan (SAP) for study LPS16872 is based on the protocol version 1 dated 11-May-2021. There are no major changes to the statistical analysis features in this SAP compared to those in the protocol.

This SAP will be finalized before efficacy review.

**Table 1 - Major changes in statistical analysis plan**

SAP Version	Approval Date	Changes	Rationale
1.0	22NOV2022	Not Applicable	Original version

[figure not shown]
# 1 INTRODUCTION

## 1.1 STUDY DESIGN

This is a 52-week, Phase 4, open-label, single-arm, multicenter study to assess the efficacy and safety of dupilumab as monotherapy without concomitant intranasal corticosteroid (INCS) in approximately 25 participants 18 years and older with chronic rhinosinusitis with nasal polyposis (CRSwNP) not adequately controlled with existing therapies.

After a screening phase of 2 to 4 weeks, participants will be treated with dupilumab 300 mg q2w without concomitant administration of INCS for approximately 24 weeks. For participants who have stable disease, the dosing interval can be changed from q2w to q4w at the discretion of the Investigator at Week 24. Participants who change from q2w to q4w will not be permitted to return to the q2w regimen during this study and will receive the q4w regimen until Week 48. Other participants will receive the q2w regimen up to Week 50. The participants will be followed up to Week 52.

Figure 1 - Graphical study design

Study analysis will be conducted after study completion.

## 1.2 OBJECTIVE AND ENDPOINTS

**Table 2 - Objectives and endpoints**

Objectives	Endpoints
Primary	

 
To assess the efficacy of 24-week treatment with dupilumab 300 mg every 2 weeks (q2w) to reduce nasal polyp score (NPS) in participants with chronic rhinosinusitis with nasal polyposis (CRSwNP) who do not use concomitant intranasal corticosteroid (INCS)
 
	
 
Proportion of participants with NPS improvement from baseline <math>\geq 1</math> at Week 24
 

Secondary	

 
To assess the efficacy of 24-week treatment with dupilumab 300 mg q2w on other efficacy endpoints in participants with CRSwNP who do not use concomitant INCS
 
To evaluate the safety of 24-week treatment with dupilumab in participants with CRSwNP
 
	
Key secondary efficacy endpoints:
 
 
Change from baseline to Week 24 in bilateral NPS
 
Change from baseline to Week 24 in nasal congestion/obstruction (NC) symptom severity score using the CRSwNP nasal symptom diary
 
Change from baseline to Week 24 in opacification of sinuses assessed by computerized tomography (CT) scan using the Lund Mackay (LMK) score
 
 
Other secondary efficacy endpoints:
 
 
Change from baseline to Week 24: 
 
Total symptom score (TSS), a composite score derived from the nasal symptom diary (includes nasal congestion, loss of sense of smell, anterior and posterior rhinorrhea)
 
Loss of smell symptom severity score using the nasal symptom diary
 
Visual analogue scale for rhinosinusitis
 
 
 
Incidence of treatment-emergent adverse events (TEAEs), treatment-emergent serious adverse events (TESAEs), and TEAEs leading to treatment discontinuation
 

Tertiary/Exploratory	

 
To assess the efficacy of 52-week treatment with dupilumab under different dosing regimens to participants with CRSwNP who do not use concomitant INCS
 
To evaluate the safety of 52-week treatment with dupilumab in participants with CRSwNP
 
	
 
Proportion of participants with NPS improvement from baseline <math>\geq 1</math> at Week 52
 
Change from baseline to Week 52 in bilateral NPS
 
Change from baseline to Week 52 in NC symptom severity score using the CRSwNP nasal symptom diary
 
Change from baseline to Week 52 in opacification of sinuses assessed by CT scan using the LMK score
 
Change from baseline to Week 52 in TSS
 
Incidence of TEAEs, TESAEs, and TEAEs leading to treatment discontinuation
 

Abbreviations: CRSwNP: chronic rhinosinusitis with nasal polyposis; CT: computerized tomography; INCS: intranasal corticosteroid; LMK: Lund Mackay; NC: nasal congestion/obstruction; NPS: nasal polyp score; q2w: every 2 weeks; TEAE: treatment-emergent adverse event; TESAE: treatment-emergent serious adverse events, TSS: total symptom score

### **1.2.1 Estimands**

Primary estimand definitions for main endpoints are summarized below in [Table 3](#). More details are provided in [Section 4](#).

**Table 3 - Summary of primary estimand for main endpoints**

Estimands				
Endpoint Category	Endpoint	Population	Intercurrent event(s) handling strategy (The missing data handling)	Population-level summary (Analysis method)
Primary objective: To assess the efficacy of 24-week treatment with dupilumab 300 mg every 2 weeks (q2w) to reduce nasal polyp score (NPS) in participants with chronic rhinosinusitis with nasal polyposis (CRSwNP) who do not use concomitant intranasal corticosteroid (INCS)				
Primary endpoint:	Proportion of participants with NPS improvement from baseline $\geq 1$ at Week 24	PP	
The intercurrent events will be handled as follows:
 
 
Undergoing surgery for NP or receiving SCS for any reason will be considered nonresponders for time points after undergoing surgery or receiving SCS. (composite strategy)
 
 
In addition, the missing data imputation rules are as follows:
 
Patients having missing data at Week 24 will be considered nonresponders..
	The number of participants and percentage with 95% continuity corrected Wilson confidence interval (CI). No additional imputation necessary.
Primary endpoint (Supplymentary analysis)	Proportion of participants with NPS improvement from baseline $\geq 1$ at Week 24	mITT	
The intercurrent events will be handled as follows:
 
 
Undergoing surgery for NP or receiving SCS for any reason for CRSwNP will be considered nonresponders for time points after undergoing surgery or receiving SCS.
 
Receiving intranasal corticosteroids (INCS) for CRSwNP up to Week 24 : Participants will be considered as non-responders (composite strategy).
 
 
In addition, the missing data imputation rules are as follows:
 
Patients having missing data at Week 24 will be considered nonresponders.
	The number of participants and percentage with 95% continuity corrected Wilson confidence interval (CI). No additional imputation necessary.
Secondary objective: To assess the efficacy of 24-week treatment with dupilumab 300 mg q2w on other efficacy endpoints in participants with CRSwNP who do not use concomitant INCS				

Estimands				
Endpoint Category	Endpoint	Population	Intercurrent event(s) handling strategy (The missing data handling)	Population-level summary (Analysis method)
Key secondary endpoints	Change from baseline to Week 24: 
 
• Bilateral NPS
 
• NC symptom severity score
 
• LMK score
 
	PP	The intercurrent events will be handled as follows: 
 
• Taking rescue medications or undergo surgery prior to Week 24: data will be set to missing after the medication usage, and the participant's worst postbaseline value on or before the time of the medication usage or surgery will be used to impute the missing Week 24 value (for participants whose postbaseline values are all missing, the baseline will be used to impute) (hypothetical strategy)
 
• Discontinuing the treatment prematurely (Participants who did not take rescue medications or undergo surgery): all data collected after treatment discontinuation will be used in the analysis (treatment policy strategy).
 
	All imputed, complete data will be analyzed by descriptive statistics and 95% CI. The summarized mean changes obtained from each imputed dataset will be combined using Rubin's rule for a single estimate.

Estimands				
Endpoint Category	Endpoint	Population	Intercurrent event(s) handling strategy (The missing data handling)	Population-level summary (Analysis method)
Other secondary efficacy endpoints	
 
• Change from baseline to Week 24:
 
• Total symptom score
 
• Loss of smell symptom severity score
 
 Visual analogue scale for rhinosinusitis		In addition, the missing data imputation rules are as follows: 
 
• After treatment discontinuation due to lack of efficacy prior to Week 24: WOCF approach will be used to impute the missing Week 24 value if needed
 
• After treatment discontinuation due to reasons other than lack of efficacy prior to Week 24: multiple imputation approach assuming missing at random will be used to impute the missing Week 24 value, and this multiple imputation will use all participants, excluding participants who have taken rescue medications or undergone surgery on or before Week 24 and excluding participants who discontinue due to lack of efficacy on or before Week 24.
 
	

Estimands				
Endpoint Category	Endpoint	Population	Intercurrent event(s) handling strategy (The missing data handling)	Population-level summary (Analysis method)
Key secondary (Supplymentary analysis)	Change from baseline to Week 24: 
 
• Bilateral NPS
 
• NC symptom severity score
 
• LMK score
 
	mITT	
The intercurrent events will be handled as follows:
 
 
• Taking rescue medications or undergo surgery for CRSwNP prior to Week 24: data will be set to missing after the medication usage, and the participant's worst postbaseline value on or before the time of the medication usage or surgery will be used to impute the missing Week 24 value (for participants whose postbaseline values are all missing, the baseline will be used to impute) (hypothetical strategy)
 
• Discontinuing the treatment prematurely (Participants who did not take rescue medications or undergo surgery): all data collected after treatment discontinuation will be used in the analysis (composite policy strategy).
 
 
In addition, the missing data imputation rules are as follows:
 
 
• After treatment discontinuation due to lack of efficacy prior to Week 24: WOCF approach will be used to impute the missing Week 24 value if needed
 
 
After treatment discontinuation due to reasons other than lack of efficacy prior to Week 24: multiple imputation approach assuming missing at random will be used to impute the missing Week 24 value, and this multiple imputation will use all participants, excluding participants who have taken rescue medications or undergone surgery on or before Week 24 and excluding participants who discontinue due to lack of efficacy on or before Week 24.
	

Estimands				
Endpoint Category	Endpoint	Population	Intercurrent event(s) handling strategy (The missing data handling)	Population-level summary (Analysis method)
Tertiary/exploratory objective: To assess the efficacy of 52-week treatment with dupilumab under different dosing regimens to participants with CRSwNP who do not use concomitant INCS				
	Proportion of participants with NPS improvement from baseline $\geq 1$ at Week 52	PPE	
The intercurrent events will be handled as follows:
 
 
Undergoing surgery for NP or receiving SCS for any reason will be considered nonresponders for time points after undergoing surgery or receiving SCS. (composite strategy)
 
 
In addition, the missing data imputation rules are as follows: Patients having missing data at Week 52 will be considered nonresponders..
	Descriptive statistics
	
Change from baseline to Week 52 in:
 
 
Bilateral NPS
 
NC symptom severity score
 
LMK score
 
TSS score
 
		
The intercurrent events will be handled as follows:
 
 
Taking rescue medications or undergo surgery for NP prior to Week 52: data will be set to missing after the medication usage, and the participant's worst postbaseline value on or before the time of the medication usage or surgery will be used to impute the missing Week 52 value (for participants whose postbaseline values are all missing, the baseline will be used to impute) (hypothetical strategy)
 
Discontinuing the treatment (Participants who did not take rescue medications or undergo surgery): all data collected after treatment discontinuation will be used in the analysis (treatment policy strategy).
 
	Descriptive statistics

## 2 SAMPLE SIZE DETERMINATION

The EFC14280 study, which was conducted as a pivotal study for Nasal Polyposis, the proportion of responders (NPS improvement from baseline  $\geq 1$ ) at Week 24 was 62.0% in the dupilumab group. Based on this result, the target proportion of responders (NPS improvement from baseline  $\geq 1$ ) at Week 24 in this postmarketing study is at least 50.0% to reflect the similar effect size between EFC14280 and this study.

It is necessary for 20 participants to achieve this response rate (at least 50%) with a 90% probability of success. The sample size was adjusted up to 25 to account for a 20% drop-out rate.

### 3 ANALYSIS POPULATIONS

The following populations for analyses are defined in [Table 4](#).

**Table 4 - Populations for analyses**

Population	Description
Screened	All participants who signed the informed consent form (ICF).
Enrolled	The enrolled population includes all participants with a treatment kit number allocated and recorded in the interactive response technology (IRT) database, regardless of whether the treatment kit was used or not. Participants treated without a treatment kit number being allocated will not be considered enrolled and will not be included in any efficacy population.
Intent-to-treat (ITT)	Enrolled population with chronic rhinosinusitis with nasal polyposis (CRSwNP)
Modified ITT (mITT)	All participants in ITT allocated to study intervention administered at least 1 dose of study intervention
Per-protocol (PP)	All participants in mITT allocated to study intervention administered at least 1 dose of study intervention, and who did not receive intranasal corticosteroids (INCS) up to Week 24
Per protocol with extension term (PPE)	All participants in mITT allocated to study intervention administered at least 1 dose of study intervention during the intervention period after Week 24, and who did not receive INCS throughout the study
Safety (SAF)	All participants allocated to study intervention administered at least 1 dose of study intervention before Week 24
Safety for extension term (SAFE)	All participants allocated to study intervention administered at least 1 dose of study intervention during the intervention period after Week 24
Population without trial impact (disruption) due to COVID-19	A Population without trial impact (disruption) due to COVID-19 is defined as any participant in randomized population: - without any critical or major deviation related to COVID-19 - and who didn't permanently discontinue treatment due to COVID-19 - and who didn't permanently discontinue study due to COVID-19.

Abbreviations: CRSwNP: chronic rhinosinusitis with nasal polyposis; ICF: informed consent form; INCS: intranasal corticosteroids; IRT: interactive response technology; ITT: intent-to-treat; mITT: modified ITT; PP: per protocol; PPE: per protocol with extension term; SAF: safety; SAFE: safety for extension term

Efficacy analyses for the treatment period up to Week 24 will be performed using the per protocol (PP) population. Efficacy analyses for the treatment period after Week 24 will be performed using the per protocol with extension term (PPE) population. Additionally, supportive efficacy analyses will be performed using the modified intent-to-treat (mITT) population.

Safety analyses for the treatment period up to Week 24 will be performed using the Safety population, including all participants allocated to study intervention and administered at least one dose of study medication prior to Week 24. Safety analyses for the treatment period after Week 24 will be performed using the Safety for extension term population, including all participants allocated to study intervention administered at least 1 dose of study intervention after Week 24.

Participants exposed to study intervention before or without being enrolled will not be considered enrolled and will not be included in any analysis population. The safety experience of these participants will be reported separately.

Enrolled participants for whom it is unclear whether they took the study intervention will be considered as exposed and will be included in the safety populations.

For any participant enrolled more than once, only the data associated with the first enrollment will be used in any analysis population. The safety experience associated with any later enrollment will be reported separately.

Regarding the COVID-19 pandemic, additional summaries by COVID-19 subgroups will be provided to assess the impact of the COVID-19 on treatment effect. Participants impacted by the COVID-19 pandemic are defined as randomized participants with any critical or major deviation related to COVID-19 or who permanently discontinued study intervention or study due to COVID-19.

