Participants who receive any of the prohibited treatments or undergo surgery during the Screening Period will not start the intervention period. They may, however, be rescreened following the procedures described in the SoA ([Section 1.3](#)).

Participants who use INCS between Visit 2 and Week 24 for whatever reason will discontinue the IMP administration.

Permitted concomitant medication

The following treatments are allowed throughout the study unless otherwise specified:

- Intranasal corticosteroids to treat other coexisting diseases (such as allergic rhinitis) are allowed after Week 24 as needed.
- Nasal normal saline.
- Single topical decongestant administration such as oxymetazoline hydrochloride (to reduce swelling and widen the path for the endoscope) and topical anesthetics such as lidocaine are allowed before endoscopy.
- Short-acting $\beta 2$ -adrenergic receptor agonists, long-acting $\beta 2$ -adrenergic receptor agonists, and long-acting muscarinic acetylcholine receptor antagonists.
- Methylxanthines (eg, theophylline, aminophyllines).
- Inhaled corticosteroids.
- Systemic antihistamines.

- Leukotriene antagonists/modifiers are permitted during the study, only for participants who were on a continuous treatment for ≥ 30 days before Visit 1.
- Allergen immunotherapy in place for ≥ 3 months before Visit 1 is permitted.
- Paracetamol/Acetaminophen, at doses of ≤ 2 g/day, is permitted for use any time during the study.

Other concomitant medication may be considered on a case-by-case basis by the Investigator in consultation with the Medical Monitor if required.

Rescue medication including antibiotics, short courses of SCS for treatment of CRSwNP as described in [Section 6.8.1](#), or short courses of SCS to treat other serious coexisting diseases (such as asthma exacerbation) or for AEs is allowed.

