## **4.6 MULTIPLICITY ISSUES**

No hypothesis testing will be performed within this study.

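### The primary Week 24 responder rate drops anyone who took INCS before Week 24 from its denominator, even when the plan's other rules would count that person as a nonresponder

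*SAP*

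**What the plan says.** SAP section 3 states: "Efficacy analyses for the treatment period up to Week 24 will be performed using the per protocol (PP) population". Table 4 limits PP to mITT participants who had at least one dose "and who did not receive intranasal corticosteroids (INCS) up to Week 24", with no restriction on the reason for INCS. Protocol Table 5 has the same definition, and SAP 4.3.5 confirms that INCS users are not in PP.

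Within PP, SAP 4.3.2 and protocol 9.3.2 count three things as nonresponse: nasal polyp surgery, SCS for any reason, and a missing Week 24 value. INCS is not on that list because its users have already been removed.

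Protocol 6.8 adds: "Participants who use INCS between Visit 2 and Week 24 for whatever reason will discontinue the IMP administration".

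The SAP also plans an mITT version of the responder analysis. In Table 3, for INCS taken for CRSwNP up to Week 24, it says: "Participants will be considered as non-responders (composite strategy". Table 3 and section 4.3.4 label that analysis supplementary.

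The target is an observed rate of at least 50%. Protocol section 9 bases the similarity conclusion on point estimates, and SAP 4.6 states: "No hypothesis testing will be performed within this study".

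**The concern.** The population for the main result depends on what participants do after treatment starts. Similar events are also handled in opposite ways: SCS for any reason keeps a participant in the denominator as a nonresponder, while INCS for any reason takes the participant out.

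The sharper problem is the overlap. Someone who takes INCS and also receives SCS, has surgery, or has no Week 24 endoscopy meets the plan's own nonresponse rule, but is deleted before the rule can apply. Protocol 7.2 encourages participants who stop treatment to remain in the study, so INCS started after stopping dupilumab can be recorded and can trigger the deletion.

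The study has no control arm and no test. With about 25 participants each one is worth about 4 percentage points (1/25), so the denominator rule can decide whether the 50% target is met.

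**Working it through.** **Inputs.** Benchmark: "at Week 24 was 62.0% in the dupilumab group" (SAP section 2). Criterion and size: "It is necessary for 20 participants to achieve this response rate (at least 50%) with a 90% probability of success", and "The sample size was adjusted up to 25 to account for a 20% drop-out rate". The number of INCS users before Week 24, k, is not given; I take 0 to 5 of 25 as an assumed range.

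**1. The plan's own figure.** With a true rate of 62% and 20 participants, P(X ≥ 10) = 0.908 by exact binomial, which agrees with the stated 90%. Inflation for dropout: 20/(1 − 0.20) = 25. The sample-size statement reproduces.

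**2. How each participant is handled in the primary analysis.**

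| Before or at Week 24 | Without INCS | With INCS as well |
|---|---|---|
| SCS | nonresponder | deleted |
| Nasal polyp surgery | nonresponder | deleted |
| Missing Week 24 value | nonresponder | deleted |
| None of these, NPS improved by ≥ 1 | responder | deleted |
| None of these, NPS not improved by ≥ 1 | nonresponder | deleted |

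The right-hand column loses both failures and successes. The direction of the error therefore depends on who the INCS users are.

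**3. If INCS users are all nonresponders.** With x responders among the others, the PP rate is x/(25 − k) and the composite rate is x/25. Their ratio is 25/(25 − k): 1.04, 1.09, 1.14, 1.19 and 1.25 for k = 1 to 5. For x = 12, with continuity-corrected Wilson 95% intervals:

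- k = 0: 12/25 = 48.0% (28.3 to 68.2)
- k = 1: 12/24 = 50.0% (29.6 to 70.4)
- k = 2: 12/23 = 52.2% (31.1 to 72.6)

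The intervals overlap almost completely, but the criterion uses the point estimate. At the far end of the assumed range, k = 5 and x = 10 give 10/20 = 50.0% against 10/25 = 40.0%.

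**4. If INCS users are responders.** Suppose two participants take INCS for allergic rhinitis, both respond, and 11 of the other 23 respond. PP gives 11/23 = 47.8%. Counting all 25, with only INCS for CRSwNP treated as nonresponse, gives (11 + 2)/25 = 52.0%. Here PP understates the rate.

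**5. Chance of reaching 50%.** Assume 62% response among the 25 − k participants without INCS, and nonresponse in all k users. PP needs at least half of 25 − k; the composite needs 13 of 25.

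| k | PP | Composite |
|---|---|---|
| 0 | 0.89 | 0.89 |
| 1 | 0.92 | 0.84 |
| 2 | 0.88 | 0.78 |
| 3 | 0.91 | 0.70 |
| 4 | 0.87 | 0.60 |
| 5 | 0.91 | 0.49 |

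Under this assumption the PP result hardly responds to how many participants leave monotherapy for INCS.

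**6. How much is discreteness.** An even denominator allows exactly 50%; 25 does not. At a true rate of 45% with no bias at all, P(observed ≥ 50%) is 0.306 for n = 25 and 0.385 for n = 24. With one nonresponding INCS user and an all-treated rate of 45%, the rate among the other 24 is 0.45 × 25/24 = 0.469, and the PP probability is 0.458. So about half of the rise from 0.306 to 0.458 is due to the even denominator. The 45% is itself an assumption, chosen just below the threshold.

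**The case against.** The strongest reply has five parts.

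- **INCS is not the plan's failure route.** Protocol 6.8.1 lists SCS, antibiotics and sinonasal surgery as rescue. INCS is prohibited before Week 24 and is off-label for CRSwNP in Japan. The INCS use that section 6.8 does mention is for coexisting disease such as allergic rhinitis. This stands, and it is why the direction of bias cannot be asserted.
- **Stopping treatment is not nonresponse.** A reader might infer from section 6.8 that an INCS user, having had to stop dupilumab, cannot be a responder. The documents do not support that. The primary analysis does not score treatment discontinuation as nonresponse, first INCS use may fall close to Week 24, and protocol 2.3.2 describes INCS efficacy in the Phase 3 studies as extremely limited.
- **PP matches the objective's wording,** which concerns participants not using INCS. This is true, but it does not explain why a participant with SCS, surgery or a missing value should disappear because INCS was also taken.
- **The mITT result will be reported anyway.** This stands and reduces the harm. It leaves open which rate is judged against 50%.
- **Consistency with EFC14280.** SAP Appendix 2 limits nonresponder imputation to surgery and SCS for this reason. But dupilumab was given with INCS in that study, so its rules cannot settle how INCS use should count here.

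**Conclusion.** The point holds as a should-fix. The primary denominator is selected on a post-baseline event, and the selection overrides the plan's own nonresponder rule for anyone who combines INCS with SCS, surgery or missing Week 24 data. If INCS users are mostly nonresponders, one or two of them can carry the estimate from 48.0% to 50.0% or 52.2%. That size rests on two assumptions that the documents do not supply: that some participants use INCS before Week 24, and that they do not respond. With no users, PP and mITT coincide. If the users are responders, PP is too low.

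Two stronger conclusions should not be drawn. One is that the planned primary result is bound to be inflated; neither the INCS rate nor the direction of bias is known. The other is that INCS for any reason should count as nonresponse because section 6.8 stops treatment whatever the reason. That section governs dosing, not scoring, and SAP Table 3 ties nonresponse to INCS taken for CRSwNP.

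**What to change.** In protocol 9.2 and 9.3.2, and in SAP section 3, section 4.3.2 and Table 3:

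1. Make the planned mITT composite responder rate the primary analysis and the one judged against 50%. Count as nonresponse INCS for CRSwNP up to Week 24 (as in Table 3), and SCS for any reason, nasal polyp surgery and missing Week 24 data (as in section 4.3.2).
2. Reconcile Table 3 with SAP 4.3.4. Table 3's mITT row describes SCS as both for any reason and for CRSwNP, and section 4.3.4 leaves unclear whether the CRSwNP qualifier covers INCS and SCS or only surgery.
3. Report how many participants used INCS before Week 24, and why.
4. Add a sensitivity analysis in which INCS for other conditions also counts as nonresponse.
5. Keep PP as supplementary.

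No new data or participants are needed, and the main computation is already planned. The cost is more than an edit: changing the primary population amends the protocol, which under protocol 10.1.1 needs IRB approval and, if the change is substantial, health authority approval. The headline rate may also be slightly lower.
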